3. **Treatment modalities that improve proprioception may reduce impulsive loading.** We evaluated the effects of stochastic resonance electrical stimulation (SR) on proprioception and gait biomechanics in individuals with knee OA (n=52). Impulsive loading was quantified from the loading rates of the peak vertical ground reaction force (vGRF) and heel strike transient (HST). The HST is a rapid, transient rise in the vGRF which occurs shortly following ground contact during gait that is indicative of impulsive loading. SR improved proprioception and altered gait biomechanics in manners that may slow knee OA progression. Specifically, SR increased the knee flexion angle at ground contact, decreased quadriceps/hamstring coactivation, and decreased impulsive loading (Figure 4). *These findings demonstrate that modalities that improve proprioception potentially reduce impulsive loading.* We anticipate that WBV and LMV will both improve proprioception in individuals who have undergone ACLR, thus altering gait biomechanics in manners that would reduce the risk of developing knee OA.

**Figure 4:** SR improved knee proprioception and reduced impulsive loading as evidenced by significant\*decreases in the loading rates (Body Weight/s) of the heel strike transient (HST) and peak vertical ground reaction force (vGRF) compared to the Control/no SR condition.

[figure not shown]

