## 3 INVESTIGATIONAL PLAN (brief overview)

### 3.1 Study Design

This preclinical investigation will utilize a single-blind randomized controlled experimental design whereby 75 individuals who have undergone ACLR will be randomly assigned to WBV, LMV, and Control groups (Figure 5). This convenience sample will include individuals recruited from two local orthopaedic clinics (UNC Department of Orthopaedics and Triangle Orthopaedic Associates), local rehabilitation clinics, and the University population, as well as veterans recruited from the Veterans Affairs Medical Center in nearby Durham, NC. Quadriceps function, proprioception, and walking gait biomechanics will be assessed prior to and following vibratory treatments (LMV or WBV) or a Control intervention. The WBV and LMV groups will

receive a single session of vibratory stimuli which we previously demonstrated to enhance quadriceps function. The Control group will perform identical procedures, but no vibratory stimulus will be applied.

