## **4 STUDY PROCEDURES (what will be done)**

Subjects will report to the UNC Neuromuscular Research Laboratory for three separate sessions. During Session 1, subjects will complete the approved informed consent document, as well as the Self-Report Surveys, Gait Biomechanics Assessment, and Quadriceps Function Assessment described below. These procedures will be used to determine if subjects meet the inclusion criteria, familiarize the subject with the testing procedures, and establish parameters necessary for the subsequent testing sessions to expedite data collection. Upon reporting to the laboratory for Session 2, subjects will perform a 5 minute warm up on a stationary cycle ergometer at a self-selected pace to reduce the likelihood of injury. They will then be fitted with motion capture markers and electromyography (EMG) electrodes followed by the Gait Biomechanics and Quadriceps Function assessments. They will then perform the respective intervention to which they have been assigned, followed by post-test measures of the aforementioned assessments. Procedures for Session 3 will be identical with the exception that the Proprioception/Sensory Assessment described below will be performed prior to and following the interventions. Sessions 2 and 3 will be separated by 1-week washout periods, and the order of these sessions will be counterbalanced.

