## **4.2 Intervention/Treatment procedures**

### **Vibratory Interventions**

All interventions will be performed with subject standing on a WBV device in approximately 40° of knee flexion, but the WBV device will only be "on" for the WBV group. Subjects assigned to the WBV group will receive a vibratory stimulus (30Hz, 2g) applied for 1 minute. This exposure will be repeated 6 times with 2 minutes of rest between exposures. Subjects in the LMV group will receive an identical stimulus (30Hz, 2g) via a custom-built vibrator secured over the distal anterior thigh. We have previously

demonstrated that these interventions enhance quadriceps activity. Subjects in the Control group will perform these exact same procedures with the exception that no vibratory stimulus will be applied. All interventions will be conducted by a graduate research assistant, and the PI will be blinded to group assignment.

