### **6.2 Statistical Methods**

**Specific Aim 1: To determine the effects of WBV and LMV on quadriceps function, proprioception, and gait biomechanics in individuals with ACLR.**

Analyses for Aim 1 will be performed using pre-post change scores for quadriceps function, proprioception, and gait biomechanics as dependent variables in separate statistical models. Mean change scores will be compared across groups (WBV, LMV, and Control) via one-way analysis of covariance (ANCOVA). Dunnett's procedure will be used to evaluate each the least-squares means for each of the intervention arms (WBV and LMV) versus control in a relatively powerful manner while controlling the overall significance level at two-sided 0.05. The corresponding pre-test values for each dependent variable will be managed as a covariate in these models to increase precision of the treatment effects, as well as to account any random imbalances among the groups with respect to these pre-scores. Other covariates would include variables with random imbalances across the groups measured at the pre-test.

The number of individuals who display HST prior to and following the intervention (or control) will be compared via McNemar's test. This analysis produces a  $\chi^2$  statistic for paired samples (i.e., the proportion with HST at pre-test vs. post-test, separately for each group).

**Specific Aim 2: To compare the effects of WBV and LMV on quadriceps function, proprioception, and gait biomechanics in individuals with ACLR.**

Aim 2 will be evaluated using the statistical models described above for Aim 1, but with focus on the statistical contrast of WBV versus LMV. Specifically, the pre-post change scores for each dependent

variable, adjusted for covariates, will be tested for the pairwise comparison of WBV versus LMV at the two-sided 0.05 significance level.

**Specific Aim 3: To identify factors that predict the effects of LMV and WBV on quadriceps function, proprioception, and gait biomechanics in individuals with ACLR.**

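### Heel-strike-transient (HST) presence is tested only pre-post within each arm, so vibration is never compared with the randomised Control on this measure

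*Combined protocol and SAP*

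**What the plan says.** Under Specific Aim 1, section 6.2 treats two kinds of outcome differently.

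- **Change-score outcomes** (quadriceps function, proprioception, gait biomechanics). These are compared across the three arms by ANCOVA with the pre-test value as covariate. Dunnett's procedure then compares the "least-squares means for each of the intervention arms (WBV and LMV) versus control", holding the overall two-sided level at 0.05.
- **HST presence.** "The number of individuals who display HST prior to and following the intervention (or control) will be compared via McNemar's test". The next sentence says that this gives a chi-square statistic for paired samples and defines the comparison as "the proportion with HST at pre-test vs. post-test, separately for each group".

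Aim 2 reuses the Aim 1 models on change scores and adds nothing for HST presence. No other section compares HST presence between arms, and no significance level or reading rule is given for the three McNemar tests.

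Control is randomised and concurrent, with 25 per arm (sections 3.1 and 3.2). Section 4.2 says of it: "Subjects in the Control group will perform these exact same procedures with the exception that no vibratory stimulus will be applied".

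**The concern.** Aim 1 asks what vibration does. Control goes through the same session without vibration, so that whatever the session itself does to gait can be subtracted. A within-arm McNemar test subtracts nothing. It asks only whether HST changed from before to after in that arm.

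Section 4 places gait testing and maximal quadriceps contractions before the intervention; then "They will then perform the respective intervention to which they have been assigned, followed by post-test measures of the aforementioned assessments". Section 4.2 has every arm stand in knee flexion on the platform during the intervention. The documents do not say whether this sequence changes HST, or in which direction. Any change it does cause appears in all three arms and stays in each within-arm result.

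The natural misreading is that HST fell significantly with WBV, did not fall significantly in Control, and so WBV reduced HST. That sets two p-values side by side and is not a test of a difference. The measure is likely to attract attention: section 1.4 presents HST as a sign of impulsive loading, and section 13 plans a primary manuscript on gait biomechanics.

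**Working it through.** The plan gives no HST rate, effect size or power, so there is no figure of its own to reproduce. The check has two parts.

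**1. Does any planned method compare HST presence between arms?** ANCOVA with Dunnett (Aim 1) and the WBV-LMV contrast (Aim 2) both act on mean pre-post change scores. HST presence is set apart with its own paired test, applied arm by arm. So no planned method does.

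**2. How often could the three tests mislead when vibration does nothing?**

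Input from the documents: 25 per arm.

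Assumed inputs: pre-test HST 50%; among those without HST, 10% gain it; among those with HST, 10%, 20%, 30% or 40% lose it; the same in all three arms. Also assumed, because the plan states no rule: a vibration effect is claimed if at least one vibration arm has p < 0.05 and Control does not.

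For each arm, share losing = pre × loss, and share gaining = (1 − pre) × gain. With 30% loss these are 0.5 × 0.3 = 0.15 and 0.5 × 0.1 = 0.05. That is a net fall of 10 points and 25 × 0.20 = 5 expected changers per arm.

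Let R be the chance of McNemar p < 0.05 in one arm, from exact enumeration of the trinomial (lost, gained, unchanged). The arms are independent, so

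P(false claim) = [1 − (1 − R)²] × (1 − R).

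For R = 0.188: (1 − 0.812²) × 0.812 = 0.341 × 0.812 ≈ 0.28.

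| Loss among HST-positive | Net fall in every arm | Expected changers per arm | R, uncorrected | False claim, uncorrected | R, corrected or exact | False claim, corrected or exact |
|---|---|---|---|---|---|---|
| 10% | 0 points | 2.5 | 0.022 | 4.3% | 0.0009 | 0.2% |
| 20% | 5 points | 3.75 | 0.081 | 14.3% | 0.0125 | 2.5% |
| 30% | 10 points | 5.0 | 0.188 | 27.6% | 0.063 | 11.5% |
| 40% | 15 points | 6.25 | 0.315 | 36.3% | 0.165 | 25.3% |

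For scale, a test with exactly 5% error in each arm would give (1 − 0.95²) × 0.95 = 9.3% under the same rule.

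*Sensitivity to prevalence*, at 30% loss and 10% gain: pre-test HST of 30%, 50% or 70% (net falls of 2, 10 and 18 points) gives 9%, 28% or 38% uncorrected, and 1.2%, 11.5% or 34% corrected or exact.

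*Version of the test.* If all changes go one way, p < 0.05 needs at least 4 changers with the uncorrected test and 6 with the corrected or exact test. With 2.5 to 6.25 changers expected, that choice can decide the result.

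*Between-arm comparison.* In the same four 50% scenarios (20,000 simulated trials each), post-test HST was compared between arms stratified by pre-test HST, with the two Control contrasts at 0.025 each. A false claim occurred in 1.5% to 2.6% of trials with the exact conditional test and in 2.8% to 4.2% with Cochran-Mantel-Haenszel. At 0.05 each, without adjustment, Cochran-Mantel-Haenszel gives 7.7% to 8.9%, so the two contrasts do need a multiplicity rule.

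**The case against.** The strongest reply is that little hangs on this measure. The plan does not rank HST presence, the Synopsis omits it from the efficacy evaluations, and no sample size rests on it. Impulsive loading is already compared with Control through the ground-reaction-force loading rates. This stands, and it limits the point to one non-primary yes/no measure. It does not supply the missing comparison.

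Second, the harm needs a shift common to all arms, and the documents report none. Subjects are not selected on HST, so eligibility does not build in regression to the mean on it directly. The larger percentages need falls of 10 points or more after one short session. The plan also never says that a significant vibration arm with a non-significant Control will be read as an effect, and testing Control would make a shift visible. All of this is fair, and the percentages are illustrations, not expected error rates. But seeing a shift in Control does not remove it from the vibration arms, and the plan offers no other way to read the three tests.

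Third, the chi-square wording points away from the exact McNemar test. That is right as far as it goes; the continuity correction is still unstated, and the table shows that it matters.

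Fourth, part of the gap between the two approaches comes from multiplicity: unadjusted between-arm tests (7.7% to 8.9%) exceed uncorrected McNemar at zero shift (4.3%). That is also right. The difference lies in how they respond to a shift: the between-arm error stays almost flat, while the McNemar pattern climbs to 36%.

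Finally, a between-arm test has low power at 25 per arm. Ignoring any gain from adjusting for pre-test HST, power at 0.025 per contrast is 21% for 50% versus 30%, 49% for 50% versus 20%, and 83% for 50% versus 10%. That is a reason to report an interval. It does not make a within-arm test evidence about vibration.

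**Conclusion.** The concern holds. For HST presence, the plan does not use its randomised Control and produces no estimate, interval or valid test of WBV or LMV against it. This follows from the text alone and needs no assumption.

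The numerical consequence is conditional. On the assumed rates, the misleading pattern has a chance of 14% to 36% (uncorrected) or 2.5% to 25% (corrected or exact) for common falls of 5 to 15 points from a 50% pre-test prevalence. With no common shift there is no excess.

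Conclusions on quadriceps function, the primary outcome in section 6.3, and on the continuous gait outcomes are not affected. The plan should be corrected, but the trial does not depend on it.

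**What to change.** In section 6.2, replace the HST sentences with a between-arm analysis:

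- Logistic regression of post-test HST (present or absent) on arm, adjusted for pre-test HST. Use an exact or Firth-penalised fit, because cells will be small. Another baseline-adjusted between-arm method, such as an exact test stratified by pre-test HST, would also serve.
- WBV-Control and LMV-Control contrasts, each with a confidence interval and with a stated multiplicity adjustment for the two.
- Within-arm McNemar results kept as description only, naming the version used, with a statement that they will not be read as evidence of a vibration effect.

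The cost is a wording change and a little more analysis on data already being collected. The intervals will be wide at 25 per arm, and the text should say that only large differences are likely to be detected.

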## PROTOCOL SYNOPSIS

Study Title	Vibratory Stimuli: A Novel Rehabilitation Method for Preventing Post-Traumatic Knee Osteoarthritis
Funder	US Department of Defense
Clinical Phase	Phase II
Study Rationale	
Anterior cruciate ligament injury and reconstruction surgery (ACLR) dramatically increase the risk of developing knee osteoarthritis (OA). Individuals with ACLR possess deficits in quadriceps muscle function and proprioception (joint position sense) that alter knee joint loading during tasks such as walking in manners that contribute to development of knee OA. Vibratory stimuli enhance quadriceps function and proprioception and may, therefore, reduce the risk of knee OA. The purposes of this study are to 1) evaluate and compare the effects of whole body vibration (WBV) and local muscle vibration (LMV) on quadriceps function, knee joint proprioception, and walking gait biomechanics in individuals with ACLR and 2) identify characteristics that determine the efficacy of WBV and LMV for improving quadriceps function, knee joint proprioception, and walking gait biomechanics in individuals with ACLR.

Study Objective(s)	
Primary
 
 
• To determine the effects of WBV and LMV on quadriceps function, proprioception, and gait biomechanics in individuals ACLR
 
• To compare the effects of WBV and LMV on quadriceps function, proprioception, and gait biomechanics in individuals ACLR
 
• To identify factors that predict the effects of LMV and WBV on quadriceps function, proprioception, and gait biomechanics in individuals ACLR
 

Test Article(s)	WBV or LMV delivered at a frequency of 30Hz and intensity of 2g
Study Design	
This preclinical investigation will utilize a single-blind randomized controlled experimental design whereby 75 individuals with primary unilateral ACLR will be randomly assigned to WBV, LMV, and Control groups. Stratified randomization into 3 groups of equal size (<math>n = 25</math>) will be performed using a computer generated randomization algorithm to ensure stratification with respect to age and time since ACLR.

Subject Population	Inclusion Criteria
key criteria for Inclusion and Exclusion:	
 
1. Subjects age 18-35
 

---

2. Undergone primary unilateral ACLR within 6 months to 5 years of participation

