Aim 3 will be evaluated using multiple regression models. Pre-post change scores for each dependent variable will be included only for the WBV and LMV groups. We will then calculate simple correlations between these change scores and the pre-test values separately for quadriceps function, proprioception, and the KOOS. We hypothesize that individuals with greater quadriceps dysfunction and proprioceptive deficits combined with lower KOOS scores (i.e. greater pain, symptoms, etc.) will display greater improvements. Separately for each dependent variable, these variables will then be placed into a stepwise multiple regression model (starting with a forward selection step). In this way, the variable with the strongest relationship with the change score will be entered first, followed by the next strongest (after adjusting for the first), etc. The model selection will stop when no additional variables are identified to enter to leave the model at the 0.10 significance level. This less conservative significance level is selected to cast a wide net to include relevant candidate terms. Next, we will examine each of these terms, one-at-a-time, as an independent variable in another regression model where the change score is the dependent variable; an indicator term for the intervention (WBV vs. LMV) will also be included as an explanatory variable, as well as the interaction between the intervention indicator and the candidate term. The initial focus will be on the significance of the interaction term, as this will determine whether the effect of the candidate term is homogeneous (reflected by non-significance of the interaction at the 0.05 level) across the interventions, or not. If the test is non-significant, the interaction term will be removed and the model refitted; the candidate term is then assessed from this model regarding its ability to predict the homogeneous effect of LMV and WBV on the corresponding dependent variable. If the interaction test is instead statistically significant, then the interaction term is retained in the model, and statistical contrasts will be constructed to estimate and test the separate effects of the candidate term by intervention group.

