## **13 PLANS FOR PUBLICATION**

We intend to draft 3 primary manuscripts for publication that will detail, respectively, 1) the effects of the interventions on gait biomechanics, 2) the effects of the interventions on somatosensory function, and 3) patient characteristics that influence the efficacy of the interventions.

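### Aim 3 leaves out the Control group, so it cannot tell predictors of the vibration effect from predictors of any pre-post change

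*Combined protocol and SAP*

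**What the plan says.** The Protocol Synopsis lists this among the primary objectives: "To identify factors that predict the effects of LMV and WBV on quadriceps function, proprioception, and gait biomechanics in individuals ACLR". Section 6.2 repeats it as Specific Aim 3, and Section 13 plans a manuscript on "patient characteristics that influence the efficacy of the interventions".

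The Aim 3 analysis in Section 6.2 runs as follows:

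- **Data:** "Pre-post change scores for each dependent variable will be included only for the WBV and LMV groups". That is 25 + 25 = 50 of the 75 subjects.
- **Candidates:** "We will then calculate simple correlations between these change scores and the pre-test values separately for quadriceps function, proprioception, and the KOOS". They then go into a stepwise regression at the 0.10 level.
- **Interaction:** each selected candidate is tested for interaction with WBV versus LMV at 0.05.
- **Reading:** without a significant interaction, the term is dropped and "the candidate term is then assessed from this model regarding its ability to predict the homogeneous effect of LMV and WBV". With one, separate slopes are estimated for WBV and LMV.

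The expected direction is stated: "We hypothesize that individuals with greater quadriceps dysfunction and proprioceptive deficits combined with lower KOOS scores" will improve more. Section 3.1 says of the third arm: "The Control group will perform identical procedures, but no vibratory stimulus will be applied". In Aim 1 the pre-test enters as a covariate only, and no pre-test-by-arm term is described.

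**The concern.** The effect of vibration is a contrast with no vibration. A slope estimated only in vibrated subjects shows who changed, not who changed because of vibration. Practice, fatigue and retest variation also move scores between pre-test and post-test. The Control arm measures exactly these, and Aim 3 does not use it.

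There are two levels of difficulty.

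1. **Any candidate.** A factor that predicts change equally with and without vibration would be reported as predicting the vibration effect.
2. **Candidates that are also the outcome.** Pre-test quadriceps function and pre-test proprioception are candidates, and both domains are outcomes. Change is post minus pre, so it contains minus the predictor. Subjects with a poor pre-test tend to improve on retest, which is also what the plan hypothesises.

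The paper on patient characteristics could therefore report that a baseline deficit predicts response to vibration when the same slope exists without it. The group contrasts in Aims 1 and 2 are not affected.

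**Working it through.** **Stated figures.** The documents give no sample size, power or error rate for Aim 3. Section 6.3 covers group comparisons only, so there is no planned figure to reproduce.

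**Inputs from Section 6.2 and Section 3.2.** 25 per group; stepwise level 0.10; WBV-versus-LMV interaction at 0.05.

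**Assumptions.** Pre-post correlation ρ of 0.70 to 0.95; equal pre and post variances (set to 1); three candidates correlated 0.3 with one another; a final test at 0.05; the same shift in both vibrated arms and no true predictor of the vibration effect.

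**Coupling of change with its own pre-test.** Write post = ρ·pre + error.

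- Change = post − pre = −(1 − ρ)·pre + error, so the slope is −(1 − ρ).
- Var(change) = 2(1 − ρ).
- Corr(pre, change) = −(1 − ρ)/√[2(1 − ρ)] = −√[(1 − ρ)/2].
- For ρ = 0.80 this is −√0.10 = −0.32. With 50 subjects, |r| above 0.235 passes the 0.10 level and above 0.279 the 0.05 level.

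**Planned steps, simulated (10,000 trials per ρ).**

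| Assumed ρ | 0.70 | 0.80 | 0.90 | 0.95 |
|---|---|---|---|---|
| Slope of change on own pre-test | −0.30 | −0.20 | −0.10 | −0.05 |
| Correlation with change | −0.39 | −0.32 | −0.22 | −0.16 |
| Own pre-test declared a common predictor | 74% | 57% | 31% | 17% |
| Same, also counting arm-specific slopes | 79% | 61% | 33% | 19% |

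The other two candidates are each declared in about 5%. With the 25 Controls added, the test of pre-test by vibration versus Control rejects in 4.7% to 5.2%. The slope is the same in Control, so it cancels.

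A separate simulation with uncorrelated candidates (4,000 trials per setting) gave 80%, 63%, 35% and 19% for the last row of the table. With no vibration effect at all and ρ = 0.80, the own pre-test was still declared in 61%.

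**Candidates without coupling.** Suppose KOOS correlates 0.2, 0.3 or 0.4 (assumed) with change, equally in all three arms. The planned steps declare it a common predictor of the vibration effect in 26%, 53% or 78% of trials (5,000 each). The interaction with Control rejects in 4.4% to 4.9%. If KOOS is unrelated to change, the planned rate is about 5%.

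**The case against.** Several points on the other side carry weight.

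- **The WBV-versus-LMV interaction is a sound randomised test.** Practice, fatigue and regression to the mean common to both arms cancel, and a real slope difference means the factor modifies the effect of at least one modality. This stands. The defect lies in the common-effect reading and in the separate arm slopes.
- **The size depends on undocumented inputs.** The expected slope is ρ × (post SD/pre SD) − 1, so a larger post-test SD shrinks it. In a simpler check (50 subjects, one test at 0.05, no stepwise step), rejection at ρ = 0.90 fell from 35% with equal SDs to 13% with a post-test SD 5% larger and 5% with one 10% larger. At ρ = 0.95 it fell from 18% to 5% with a 5% larger SD. A still larger ratio reverses the sign. At ρ = 0.70 it was still 51% with a 10% larger SD. Equal SDs are the natural null, and a smaller post-test SD makes matters worse.
- **The KOOS figures are conditional.** They assume that KOOS predicts change in Control too, which no section shows. They illustrate what the design cannot rule out.
- **The scope of the coupling depends on wording.** Section 4.1 gives three quadriceps measures (peak torque, rate of torque development, activation ratio), and Aim 3 does not say which is the predictor. If one predicts change in another, the direct coupling is absent, though measures from the same contractions may share error. Gait outcomes have no own-baseline candidate.
- **Aim 3 could be seen as screening.** The 0.10 level and the proof-of-concept framing in Section 1.3 suggest this. But the plan does not call Aim 3 exploratory, and such a label would not turn a slope in treated subjects into a predictor of efficacy.

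**Conclusion.** The concern holds. No step in Section 6.2 compares a candidate's slope with Control, so the plan cannot support the conclusion it intends to draw for an objective listed as primary. That follows from the design and needs no simulation. The size of the error does rest on assumptions: for own-baseline predictors it is about 17% to 74% across ρ from 0.95 to 0.70 with equal variances, and it approaches the nominal 5% at high ρ if the post-test SD is 5% to 10% larger. For other predictors it is near 5% unless they also predict change without vibration. The point should be corrected before the data are analysed.

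**What to change.** **Change to Section 6.2, Specific Aim 3.**

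- Fit each outcome on all 75 subjects: change (or post-test score) on the candidate, treatment (WBV, LMV, Control) and candidate-by-treatment terms. Include the outcome's own pre-test when the candidate is something else.
- Call a factor a predictor of the vibration effect only from its interaction with vibration versus Control. Keep WBV versus LMV as a secondary contrast.
- Name the quadriceps measure used as predictor.
- Report interaction estimates with 95% confidence intervals and label Aim 3 exploratory.
- Optionally, fit the hypothesised candidates directly instead of by stepwise selection.

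The minimum alternative is to relabel Aim 3, and the manuscript in Section 13, as predictors of change after vibration. That gives up the stated objective.

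**Cost.** Revised wording and some extra analysis; no new subjects, visits or measurements. The real cost is power, simulated here for an own pre-test candidate with 8,000 trials per cell:

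| Assumed ρ | 0.70 | 0.80 | 0.90 | 0.95 |
|---|---|---|---|---|
| Power, 0.3 pre-test SD extra change per SD of baseline | 37% | 49% | 75% | 95% |
| Power, 0.2 pre-test SD | 19% | 24% | 43% | 69% |
| 95% CI half-width, pre-test SD | 0.37 | 0.31 | 0.22 | 0.16 |

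By normal approximation, the slope difference detectable with 80% power is (1.96 + 0.84) × √(1/50 + 1/25) = 0.69 residual SD per SD of predictor. Fewer factors will be declared, hence the intervals and the exploratory label.

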Statistical power for the effect sizes given in Table 2 was calculated for one-tailed independent t-tests. These estimates indicate that a sample of 39-78 subjects (13-26 per group) would provide statistical power of 0.80 for  $\alpha = 0.05$  to evaluate pairwise comparisons between the Control group and each vibratory intervention (i.e. Aim 1). In contrast, 194 subjects (97 per group) would be necessary to provide adequate power to identify the relatively small effect sizes for comparing the two vibratory interventions (i.e. Aim 2). The associated mean differences in CAR between WBV and Control and between LMV and Control were 8.26% and 5.86%, respectively, while the difference between LMV and WBV was only 0.68%. Similarly, the associated mean differences in peak torque between WBV and Control and between LMV and Control were 0.29 N/kg and 0.20 N/kg respectively, while the difference between LMV and WBV was only 0.04 N/kg. These data suggest that the small mean differences in the dependent variables between WBV and LMV, even when powered sufficiently, are not likely clinically or physiologically relevant. Therefore, we will recruit a sample of 75 individuals (25 per group) to address the proposed specific aims. This sample size will provide adequate power to demonstrate similar improvements in quadriceps function with WBV and LMV.

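### Aim 3 takes a non-significant WBV-versus-LMV interaction as showing that a predictor acts alike in both arms, which 25 per arm cannot show

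*Combined protocol and SAP*

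**What the plan says.** Under Specific Aim 3, section 6.2 restricts the analysis to the vibration arms: "Pre-post change scores for each dependent variable will be included only for the WBV and LMV groups". Candidates are chosen by stepwise regression: "The model selection will stop when no additional variables are identified to enter to leave the model at the 0.10 significance level". Each selected term then goes, one at a time, into a model with the term, an arm indicator and their interaction. The interaction test is said to determine "whether the effect of the candidate term is homogeneous (reflected by non-significance of the interaction at the 0.05 level) across the interventions, or not".

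What follows depends on that p value. "If the test is non-significant, the interaction term will be removed and the model refitted", and the candidate is then assessed from the refitted model "regarding its ability to predict the homogeneous effect of LMV and WBV on the corresponding dependent variable". Only after a significant interaction does the plan say that "statistical contrasts will be constructed to estimate and test the separate effects of the candidate term by intervention group".

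On size, section 6.3 says "we will recruit a sample of 75 individuals (25 per group) to address the proposed specific aims". Aim 3 therefore rests on 50 people, 25 in each vibration arm. The documents state no power for the interaction test, no margin for calling two slopes alike, and no interval for their difference.

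**The concern.** A test that fails to reject equal slopes shows equal slopes only if it would have rejected important differences. The plan does not ask whether it would. It defines homogeneity as non-significance, and it makes the arm-specific results conditional on significance. The estimates that would expose a wrong conclusion are therefore left out of the planned results in the cases where the conclusion is wrong.

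Identifying predictors of response is listed among the primary objectives in the synopsis, and section 13 gives patient characteristics that influence efficacy a manuscript of their own. Section 1.3 stresses that the two modalities differ in cost and portability and says that the results should inform a larger trial. A mistaken statement that a characteristic predicts response to both modalities could carry over into that trial's design.

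**Working it through.** **The plan's own figures.** Section 6.3 gives 13 to 26 per group for vibration versus control and 97 per group for WBV versus LMV, at 80% power and 0.05. Power "was calculated for one-tailed independent t-tests". The normal approximation is n = 2(1.645 + 0.842)²/d² = 12.37/d² per group.

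- d = 0.98: 12.9, so 13.
- d = 0.70: 25.2, so 26.
- d = 0.36: 95.4, so 96. The noncentral t gives 97.

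The stated figures reproduce. None of them concerns the Aim 3 interaction. By the plan's own account, a simple mean difference between the two vibration arms needs almost four times the 25 per arm recruited (97/25 = 3.9).

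**Inputs for the interaction.** From the documents: 25 per arm, a 0.10 screen, a 0.05 interaction test, and a refit if that test is non-significant. Assumed, because the documents are silent:

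- predictor and change score both standardised;
- correlation r in one arm and 0 in the other, with r from 0.3 to 0.7;
- a two-sided interaction test, and a two-sided 0.05 level for the refitted term;
- one candidate considered alone;
- no dropout.

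**Hand check at r = 0.5.**

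- Average residual variance = [(1 − 0.25) + 1]/2 = 0.875.
- Standard error of the slope difference ≈ √(2 × 0.875/22) = 0.282.
- Noncentrality = 0.5/0.282 = 1.77, against a critical t of 2.01 on 46 df.
- Power ≈ Φ(1.77 − 2.01) = Φ(−0.24) ≈ 41%. Simulation gives 42%.

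**Simulation of the sequence.** 40,000 data sets per row: pooled screen at 0.10, interaction test on 46 df, then the common-slope refit on 47 df.

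| r in one arm (0 in the other) | Interaction power | Passes screen | Called homogeneous, of those screened in | Also significant as common predictor, of those screened in | Same outcome, of all such predictors |
|---|---|---|---|---|---|
| 0.3 | 17% | 28% | 84% | 54% | 15% |
| 0.4 | 28% | 41% | 75% | 53% | 22% |
| 0.5 | 42% | 55% | 61% | 47% | 26% |
| 0.6 | 59% | 68% | 44% | 38% | 26% |
| 0.7 | 75% | 80% | 27% | 25% | 20% |

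The last column is the product of the third and fifth. At r = 0.5, for example, 0.553 × 0.470 = 0.26.

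**Precision.** The median 95% confidence half-width for the slope difference is about 0.52 to 0.58 SD of change per SD of predictor across these rows. A non-significant estimate near zero is thus compatible with a true difference of around half an SD per SD in either direction. The difference detectable with 80% power at 25 per arm is about 0.75 to 0.86 for residual variances of 0.75 to 1. For 80% power, the five rows would need about 172, 96, 60, 40 and 30 per arm.

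**The case against.** Several points on the other side stand in whole or in part.

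- **How often the error occurs.** A reader might infer that a one-modality predictor would usually be published as predicting response to both. The figures do not support that. The outcome of homogeneous and significant occurs in 25% to 54% of such predictors that pass the screen, and in 15% to 26% of all of them, because many fail the pooled screen first. A strong one-arm predictor (r = 0.7) gives a significant interaction 75% of the time.
- **Whether slopes are estimated.** A reader might infer that the arm-specific slopes are never obtained. They are: the interaction model is fitted for every candidate before any term is removed. The gap is in what is interpreted and reported.
- **What Aim 3 asks.** The aim concerns factors that predict the effects of LMV and WBV, and the stated hypothesis (worse function, proprioception and KOOS scores predict more improvement) is common to both. The documents do not set Aim 3 up to decide who should receive which modality, and they give no reason to expect a slope of exactly zero in one arm. For a variable's own pre-test value, measurement error alone ties change to baseline in both arms, so the zero-slope case fits mainly predictors from another domain.
- **Simplification as practice.** Removing a non-significant interaction is common model building, and the pooled slope is the more precise test of the common hypothesis. This stands. The fault is the conclusion drawn from the removal.
- **The simulation.** It takes one candidate alone, whereas the plan uses multivariable stepwise selection, and the 0.05 level for the refitted term is assumed. The percentages illustrate the rule and are not exact properties of the plan.

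None of this supplies a ground for concluding homogeneity from non-significance. A common hypothesis is a reason to estimate a pooled slope, not evidence that the slopes are equal. The proof-of-concept framing in section 1.3 does not soften the rule either, since Aim 3 is not labelled exploratory.

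**Conclusion.** The concern holds in this form: section 6.2 states a rule under which non-significance establishes homogeneity, and 25 per arm cannot support that conclusion. Interaction power is below 80% at every one-arm correlation tried from 0.3 to 0.7. A predictor that acts in one modality only can be, and often would be, reported as common to both.

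The sizes rest on assumed slopes, a single candidate and an assumed 0.05 level for the refitted term. The logical fault does not depend on them. Claims that the error would occur in most cases, or that the refit is itself improper, go beyond what the documents and the calculation support. Aim 1 is unaffected. What changes is the conclusion that Aim 3 may draw.

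**What to change.** In section 6.2, Specific Aim 3:

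1. Remove the statement that a non-significant interaction reflects a homogeneous effect.
2. For every candidate, whatever the interaction p value, report the WBV slope, the LMV slope and their difference, each with a 95% confidence interval, from the interaction model already planned.
3. Keep the common-slope refit if wanted, but describe its coefficient as the average association over the two modalities.
4. State that a non-significant interaction does not establish a common effect.

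The cost is a change of wording and one extra table, with no new participants, visits or data. The arm-specific intervals will be wider than the pooled one, which is the precision that 25 per arm provides.
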